5.2 Study Subjects

Subject Disposition

Subject disposition will be summarized by cohort, using the number and percent of subjects who complete the study, the number and percent of subjects who discontinue the study, and the reasons for discontinuation.

Subject disposition and completion status will be listed for all enrolled subjects.

Protocol Deviations

Protocol deviations will be identified prior to database lock and may include but are not limited to: significant violations of inclusion/exclusion criteria, noncompliance of the trial treatment taken, conditions such as vomiting and diarrhea or use of prohibited medications, and not following clinical trial protocol procedures that may affect evaluation of the PK profile.

Protocol deviations will be listed by subject, cohort, and treatment for all enrolled subjects.

Subject Eligibility

Following protocol amendment, version 01 the eligibility for enrollment included subjects taking oral atorvastatin prior to the study, subjects taking statins other than atorvastatin prior to the study, and subjects not taking any statins prior to the study. A summary of these groups and cohort, final intravenous treatment, and final subcutaneous treatment will be produced. A listing by subject and cohort will be produced.

5.3 Subject Demographics

Demographics will be summarized by cohort and by IV or SC treatment in the safety population. The demographic consist of age, gender, race, and ethnicity. Individual demographics for the safety population will be listed by cohort, subject and treatment.

The age is a calculated parameter. Age will be calculated using the subject's date of birth and the subject's informed consent date.

Continuous variables (age) will be summarized by n, mean, SD, min, median, and max. Number of subjects and percentages will be used to describe categorical (discrete) variables (gender, race and ethnicity).

5.4 General Medical/Surgical History and Procedures/Non-Drug Therapies

The presence/absence of any current medical condition and/or other significant medical/surgical history will be coded using Medical Dictionary for Regulatory Activities (MedDRA) Version 22.0. Any procedures/non-drug therapies that are incurred during the course of the study will also be coded using MedDRA or World Health Organization (WHO) Drug Enhanced Dictionary (version Global B3 March 2019), as appropriate.

Medical/surgical history and procedures/non-drug therapies will be listed by cohort, subject and treatment, respectively.

5.5 Prior and Concomitant Medications

All prescription medications and over-the-counter (OTC) products, including herbal products, taken from 30 days prior to Screening until the end of treatment will be documented in the subject's source documentation and the eCRF.

Prior and concomitant medications will be recorded and coded using the current version of WHO Drug Enhanced Dictionary (version Global B3 March 2019). Prior medications will be those that start and end prior to first dose of study drug. Concomitant medications will be those that have a known end date after the first dose of study drug or have a missing end date. Medications will be listed by cohort, subject, treatment, preferred term (PT) and Anatomical Therapeutic Chemical (ATC) classification, including the start and end dates and times, dose, unit and indication.

5.6 Efficacy Analysis

Efficacy will be determined by evaluating the final cohorts for each dosing level and the ability to meet the targets of

- 11 of 13 subjects with a Day 15 LDL-C not more than 125% of their baseline LDL-C
- 11 of 13 subjects with a Day 15 HDL-C not less than 75% of their baseline HDL-C
- The mean change at Day 15 in LDL-C for each treatment cohort

The dose required to meet the targets for each cohort will be listed by subject and summarized. A dosing cohort will be considered successful if eleven or more subjects have a Day 15 LDL-C not more than 125% of their baseline LDL-C. The responders for LDL-C and HDL-C and LDL-C change from baseline in each dosing cohort will be summarized for final IV daily dose as well as each IV daily dose.

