12 STATISTICAL METHODS AND DATA ANALYSIS

12.1 Sample Size Determination

The clinical goal of replacing stable oral dosing of atorvastatin with temporary intravenous or subcutaneous dosing is to maintain constant LDL-C levels during and following the replacement therapy window. Therefore, the target mean change in LDL-C is zero. Utilizing the standard biological variabilities of LDL-C and an associated, estimated standard deviation of 0.15, a sample size of 13 would provide 80% power to show that the mean change in LDL-C after switching to intravenous or subcutaneous dosing is less than 10% of baseline levels if the true mean change for the group is zero. A mean change in LDL-C of up to 10% is not considered to be clinically significant over a short, two-week period.

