12.3.1 General Considerations

Data collected in this study will be presented using summary tables and subject data listings. Continuous variables will be summarized using descriptive statistics, specifically n (number of subjects), mean, median, standard deviation (SD), minimum and maximum. Categorical variables will be summarized by frequencies and percentages.

Statistical calculations will be done using SAS software (Version 9.3 or higher, SAS Institute, Cary, North Carolina, USA).

Baseline is considered the last assessment prior to the date and time of first dose of study drug.

Change from Baseline is defined as: post baseline assessment value – baseline assessment value.

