In a Phase 1 clinical trial in healthy volunteers, a preliminary pharmacokinetic (PK) profile for the parent compound and the two active metabolites was established for the IV delivery route. No major safety concerns were identified.

The current study is intended to further define the pharmacodynamic properties of atorvastatin and metabolites when delivered intravenously or subcutaneously, and to propose a dosing regimen to meet efficacy and safety objectives in changing from an oral to an injectable route. A single dose of atorvastatin will also be given by the subcutaneous

(SC) route in a sub-study and initial pharmacokinetic data will be collected for subjects enrolling under Amendments 1 or 2 of the study protocol. In Protocol Amendment 3, dated 03Sep2019, subjects taking oral atorvastatin change to a subcutaneous route for the treatment phase rather than an intravenous route.

This statistical analysis plan (SAP) covers the detailed procedures for performing statistical analyses and for producing Tables, Figures, and Listings (TLFs) for this study.

2 Study Objectives

The objectives of this study apply to hypercholesterolemic subjects currently being maintained on a stable dose of oral atorvastatin:

- To propose IV doses of atorvastatin injection that adequately replace each dose level of oral atorvastatin
- To describe the PK profile of atorvastatin injection administered by the IV route
- To explore the PK profile of atorvastatin administered by the SC route
- To assess the safety of the study drug administered by either the IV or SC route.

3 Study Endpoints

- To support a dose of atorvastatin injection that adequately replaces oral atorvastatin, the following primary endpoint will be evaluated for three of the four labelled oral doses of atorvastatin (10, 20, and 40 mg daily); endpoints are assessed using the subjects' levels of low-density lipoprotein cholesterol (LDL-C) and high-density lipoprotein cholesterol (HDL-C):

- Eleven or more subjects in a dosing cohort of thirteen with a Day 15 LDL-C not more than 125% of their baseline LDL-C.

Secondary endpoints that contribute to the same objective are as follows:

- Eleven or more subjects in a dosing cohort of thirteen with a Day 15 HDL-C not less than 75% of their baseline HDL-C.

- The mean change in LDL-C at Day 15 for each treatment cohort (N=13)

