4.4 Sample Size Justification

The clinical goal of replacing stable oral dosing of atorvastatin with temporary injectable dosing is to maintain constant LDL-C levels during and following the replacement therapy window. Therefore, the target mean change in LDL-C is zero. Utilizing the standard biological variabilities of LDL-C and an associated, estimated standard deviation of 0.15, a sample size of 13 would provide 80% power to show that the mean change in LDL-C after switching to injectable dosing is less than 10% of baseline levels if the true mean change for the group is zero. A mean change in LDL-C of up to 10% is not considered to be clinically significant over a short, two-week period.

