5.1 Analysis Populations

The following analysis populations will be used to summarize the results from this study.

- **Enrolled Population:** All subjects who were eligible, signed informed consent and were assigned IMP.
- **Safety Population:** All subjects who received at least a partial dose of IMP. No treated subjects will be excluded from the safety population.
- **Efficacy Population:** A completed group of subjects that 1) finished the two-week treatment period, 2) provided a Day 15 LDL-C level, and 3) took the final targeted dose for that cohort comprise the four efficacy populations.
- **Pharmacokinetic Population:** All subjects in the Efficacy Population who have no major protocol deviations and who have sufficient plasma atorvastatin concentration data for reliable estimates of the key PK variables for each of the four baseline cohorts.
- **Bioavailability Population:** All subjects in the PK Population who have complete PK profiles for either the IV or the SC multiple-dose treatment. This population will be used for the bioavailability analysis of PO/IV and PO/SC, respectively.

The frequency and percentage of subjects in each population will be summarized by cohort. Subjects who are excluded from the analysis populations will be listed by cohort, subject and treatment.

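### Each cohort of 13 is sized to show a mean LDL-C change below 10% of baseline, but no planned analysis makes that comparison, and the 11-of-13 count does not stand in for it

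*SAP*

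**What the plan says.** Protocol 12.1 gives the reason for the cohort size: "a sample size of 13 would provide 80% power to show that the mean change in LDL-C after switching to intravenous or subcutaneous dosing" stays under 10% of baseline when the true change is zero, with an estimated SD of 0.15. SAP 4.4 repeats this for injectable dosing. Both sections set the target mean change at zero, and SAP 4.4 explains the limit: "A mean change in LDL-C of up to 10% is not considered to be clinically significant over a short, two-week period".

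The primary endpoint is a count: at least 11 of 13 subjects with Day 15 LDL-C no higher than 125% of baseline (Protocol 7, SAP 3). Mean LDL-C change is a secondary endpoint. SAP 5.6 lists it as "The mean change at Day 15 in LDL-C for each treatment cohort" and then ties success to the count alone: "A dosing cohort will be considered successful if eleven or more subjects have a Day 15 LDL-C not more than 125"% of baseline. Protocol 12.3.2 also requires the HDL-C count. Neither rule uses the mean.

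Protocol 12.3.1 fixes the scale: "Change from Baseline is defined as: post baseline assessment value" minus the baseline value. SAP 4.5 does the same and limits summaries to n, means, SD, median and range. The only planned confidence interval is for pharmacokinetic ratios (SAP 5.7.3). Percent change appears only as an optional plot by IV dose (SAP 5.7.4).

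SAP 5.1 defines the efficacy groups as completers who "took the final targeted dose for that cohort comprise the four efficacy populations". The fourth is the 10-subject subcutaneous cohort. SAP 5.6 ends by saying that responders and LDL-C change are "summarized for final IV daily dose as well as each IV daily dose".

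**The concern.** The only quantified reason for 13 subjects is a comparison of the mean with 10% of baseline, and the planned efficacy analysis never makes it. The planned summary is also on a different scale. The 10% limit and the SD of 0.15 are fractions of baseline, whereas the planned change is post minus baseline in measured units.

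Protocol 5.4 and 8.1 and SAP 4 describe the intended doses as non-inferior to the oral dose, and a cohort is declared successful on counts. A reader of the report could take a successful cohort as having met the 10% limit on the mean. What is at stake is what may be claimed from a successful cohort, not which dose is established.

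**Working it through.** **Inputs.** From Protocol 12.1 and SAP 4.4: n = 13, SD = 0.15, limit = 0.10, true change = 0, power = 80%. From Protocol 7 and SAP 3: success is X ≥ 11 of 13 with a change of at most +25%. Assumed, because the documents do not say: one-sided alpha of 2.5%, 5% or 10%, and independent, normally distributed percent changes.

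**1. The plan's own figure.** n = (SD × (z(1−α) + z(0.80)) / limit)².
- At one-sided 5%: (0.15 × (1.645 + 0.842) / 0.10)² = 13.9, so 14 subjects.
- At one-sided 2.5%: 17.7, so 18 subjects.
- Normal-approximation power at n = 13 is Φ(0.10 × √13 / 0.15 − z(1−α)). At 5% this is Φ(2.404 − 1.645) = 0.776.

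| One-sided alpha | Power, normal, n=13 | Power, t, n=13 | Power, t, n=10 |
|---|---|---|---|
| 2.5% | 67% | 60% | 47% |
| 5% | 78% | 73% | 62% |
| 10% | 87% | 85% | 77% |

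The stated 80% is therefore close to a one-sided 5% normal calculation. With SD 0.145, which rounds to 0.15, that calculation gives 80.0%. If the limit applies in both directions (two one-sided 5% t tests), power at n = 13 is 47%.

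**2. Does the count do the same job?** The chance that one subject meets the criterion is p = Φ((0.25 − μ)/SD), and the cohort passes with probability P(X ≥ 11 | 13, p). At μ = 0.10 and SD 0.15, p = Φ(1.00) = 0.841. The probabilities of 11, 12 and 13 responders are 0.294 + 0.259 + 0.106 = 0.659.

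| True mean change (SD 0.15) | p | P(count met) |
|---|---|---|
| 0 | 0.952 | 97.8% |
| 5% | 0.909 | 89.1% |
| 10% | 0.841 | 65.9% |
| 15% | 0.747 | 32.5% |
| 20% | 0.631 | 8.8% |

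At a true 10% rise the pass rate is 94.9% for SD 0.10 and 40.7% for SD 0.20. A test of the 10% limit would pass such a cohort only at its alpha, for example 5%.

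**3. Allowing for the dose-increase trigger.** Protocol 9.3.6.2.2 says that three or more subjects at or above 125% on Day 8 and/or Day 15 may start an adjustment. Suppose it were always applied. In 200,000 simulated cohorts with a true Day 15 rise of 10% and SD 0.15, the pass rates for Day 8/Day 15 correlations of 0, 0.4 and 0.8 were:
- Day 8 mean +10%: 22%, 29% and 43%.
- Day 8 mean +5%: 38%, 45% and 57%.

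**4. What an upper limit would show.** The half-width of a one-sided 95% t limit is t × 0.15/√n, which is 0.074 at n = 13 and 0.087 at n = 10. The limit falls below 10% only if the observed mean is below about 2.6% (n = 13) or 1.3% (n = 10). At a true change of zero, 27% of all cohorts (1 − 0.73) and about 25% of those passing the count would not exclude 10%.

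**5. Precision of the count.** An observed 11/13 has an exact 95% interval of 55% to 98%. For comparison, 8/10 gives 0.444 to 0.975.

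**The case against.** The primary endpoint is the count. It is clearly defined, and the plan nowhere says that it shows a mean change below 10%. The study is open-label, single-arm and Phase II, and non-inferior describes the intent behind the doses, not a planned test. All of that stands, and it limits the point to reporting and interpretation.

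Several stronger readings are tempting but not supported:

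- *The mean has no target value.* It does: Protocol 12.1 and SAP 4.4 set it at zero and treat up to 10% as acceptable. What is missing is a link from the efficacy sections and an interval.
- *The sample size is wrong.* The 80% is a near miss at one-sided 5%, and 0.15 is described as an estimate. The defensible criticism is that alpha, test and direction are unstated.
- *The comparison could never be recovered.* SAP 4.5 lists all analysed subject data, so a reader could rebuild percent change and a limit. They would be doing an analysis that was not prespecified.
- *Most passing cohorts fail to exclude 10%, so the count misleads.* At a true 10% rise about 92% of passing cohorts have an upper limit at or above 10%, but so do 95% of all cohorts by construction. The informative figure is the 66% pass rate.
- *The subcutaneous cohort has no efficacy analysis.* Protocol 12.2 calls for its efficacy outputs individually, and the mean-change bullet covers every treatment cohort. The real gaps are that 11-of-13 cannot describe 10 subjects and that the last sentence of SAP 5.6 names only IV doses.

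The pass rates also depend on the model. The HDL-C count is not included, and enrolment may stop for other signs of lack of efficacy (Protocol 8.1). Day 8 and Day 15 changes share a baseline, so zero correlation is an extreme; with equal independent errors the correlation is 0.5, which gives about 32% or 47% in place of the 22% or 38% at zero correlation.

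**Conclusion.** The point holds as a gap between the sizing rationale and the planned analysis. Thirteen subjects are justified by a comparison of mean change with 10% of baseline that neither efficacy section makes, and the planned summary has no interval and is on another scale.

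Meeting 11-of-13 does not replace that comparison. A cohort with a true 10% mean rise meets the LDL-C count about 66% of the time at SD 0.15 (41% to 95% for SD 0.20 to 0.10), or about 22% to 57% if the increase trigger were always applied. These figures assume independent normal percent changes and leave out the HDL-C count.

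The power statement is incomplete rather than badly wrong: 73% (t) or 78% (normal) at one-sided 5%, and 60% or 67% at one-sided 2.5%. The primary count and its computation are unaffected. The correction is worth making because it changes what the report can say about mean LDL-C.

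**What to change.** - **SAP 5.6 and Protocol 12.3.2.** For each final cohort, report mean percent change in LDL-C at Day 15, 100 × (Day 15 − baseline)/baseline, with a t-based one-sided 95% upper limit, or the limit at whatever alpha the sponsor states for sizing. Show it beside 10%, labelled descriptive and not a success criterion. Keep 11-of-13 as primary and add its exact 95% interval. A sentence saying that the count alone does not show a mean change below 10% would help but is optional.
- **Protocol 12.1 and SAP 4.4.** State alpha, the test, and whether the limit concerns a rise only. Restate the power to match, for example 73% by t test at one-sided 5%.
- **Subcutaneous cohort.** Report the same mean percent change and limit, and the responder count out of 10 with an exact interval, without the 11-of-13 rule.
- **Timing.** LDL-C is reviewed open-label in real time (Protocol 9.3.6.2.1), and SAP Table 1 already describes the fourth cohort's dosing in the past tense. If LDL-C data have been seen, record the addition as post hoc under SAP 5.11/5.12. If the protocol can no longer be amended, put the text in the SAP.

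**Cost.** Text edits in four sections and extra columns in one table, with no new data or subjects. The stated power becomes less favourable. At SD 0.15 about 25% of truly matched cohorts that pass the count would not exclude a 10% mean rise. Reading the limit only in cohorts that passed also makes it slightly lenient: at a true 10% rise about 7.6% of them would exclude 10%, rather than 5%.

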5.7 Pharmacokinetic Analysis

The PK analysis will be conducted using WinNonlin Version 8.1 or higher (Certara, Princeton, NJ). In the PK analyses and summary statistics, all plasma concentrations below the lower limit of quantification (BQL) for the assay will be treated as “0” if they occur before the first measurable or after the last measurable concentration, and will be set as missing for data points in between two measurable concentrations.

5.7.1 Plasma Concentrations

Plasma concentrations of atorvastatin and its metabolites will be listed at each time point by cohort, subject and treatment, and summarized by route and final treatment cohort at each time point using descriptive statistics (n, arithmetic mean, SD and coefficient of variation (CV), geometric mean, geometric CV%, min, median and max).

Plots of individual concentrations of atorvastatin and its metabolites versus time, and mean plasma concentrations of atorvastatin and its metabolites versus the planned sampling time, will be presented on linear and semi-logarithmic scales.

5.7.2 Pharmacokinetic Parameters

Pharmacokinetic parameters will be derived for atorvastatin and its metabolites for subjects in the PK population.

Pharmacokinetic parameters are defined in Table 4.

Table 4: Pharmacokinetic Parameters

Parameter	Description
C_{\max}	Maximum plasma concentration
AUC_{0-24}	Area under the plasma concentration-time curve from time zero to 24 hours
AUC_{∞}	Area under the plasma concentration-time curve from time zero to infinity
T_{\max}	Time to reach maximum plasma concentration
$T_{1/2}$	Elimination half-life
K_{el}	Elimination rate constant
$Cl(/F)$	(Apparent) clearance of drug from plasma for extravascular dosing
VD_{ss}	Volume of distribution at steady state for intravenous dosing
V_z/F	Apparent volume of distribution for extravascular dosing

Pharmacokinetic parameters will be calculated using noncompartmental methods and actual blood sampling times. In case of missing actual time, planned (or nominal) time will be used.

Concentration listed as below the limit of quantitation will be set to zero for the calculations. If a sample is missing or the value is not reportable and is between two measurable concentrations, the value at that time point will be left blank for the analysis and reported as either Not Reportable (NR) or No Sample (NS).

The PK timepoint at 24-hour post oral dosing is the pre-dose concentration due to reaching steady state. The first timepoint immediately following IV bolus dosing is set as 0.0055 hour (assume 20 seconds bolus dosing). The 24-hour post-dose concentration is set as pre-dose concentration before IV and multiple-dose SC dosing. For the single dose SC (sub-study) the pre-dose concentration is the 24-hour post-oral dose concentration.

No value of K_{el} , AUC_{∞} or $t_{1/2}$ will be reported for cases that do not exhibit a terminal log-linear phase in the concentration versus time profile. If the adjusted R-squared value ($Rsq_{adjusted}$) is < 0.8 , the analyst may evaluate if other time points are more appropriate and use those for the calculation of K_{el} , or no value of K_{el} , AUC_{∞} or $t_{1/2}$ will be reported.

For determination of AUC_{∞} , if calculated AUC from last to infinity is greater than 20% of the calculated AUC from 0 to infinity, then AUC_{∞} will not be reported.

Summary statistics for PK parameters except for T_{\max} will be described by n, arithmetic mean (mean), arithmetic mean SD, arithmetic CV%, geometric mean, geometric CV%, min, median, inter-quartile range (Q1:Q3) and max. For T_{\max} , summary statistics will be described by n, median, Q1:Q3, min and max. All PK parameters will be listed by cohort, subject and treatment.

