9.3.4 Pharmacokinetic Assessments

Allowable time windows for PK draws are shown below in [Table 9-3](#). Sampling taken outside of the allowable windows still contribute to building the pharmacokinetic profile, but minor deviations are captured in the Case Report Form (CRF).

Blood samples are taken by either direct venipuncture or via an indwelling catheter; however, samples must not be taken from the same catheter or any device used for administering the study drug.

Pharmacokinetic blood samples are collected for analyzing atorvastatin and metabolite concentrations in plasma.

If blood samples are obtained from an indwelling catheter rather than direct venipuncture, the catheter must be kept patent with saline flushes. A blood sample of approximately 1 mL will be drawn and discarded prior to each saved collection.

The samples are frozen in a -20°C freezer within 120 minutes of being drawn.

The actual sample collection date and time is entered in the eCRFs. Any issues with the sampling process will be noted.

Table 9–3 Allowable Time Windows for Pharmacokinetic Draws

Route being studied	Target time of blood draw	Allowable time window
Oral (screening period)	Pre-dose	-60 to -1 minutes before a dose of oral atorvastatin is taken

	Hour 0.5	\pm 5 minutes
	Hours 1, 2, 4, 6, and 8	\pm 10 minutes
Intravenous or Subcutaneous (Day 15)	Prior to the IV or SC dose	-60 to -1 minutes before the dose of IV or SC atorvastatin is taken
	Immediately after the IV or SC dose	3 to 7 minutes following the end of the administration
	Hour 0.5	\pm 5 minutes
	Hours 1, 2, 4, 6, and 8	\pm 10 minutes
Subcutaneous (Day 22)	Hour 0.5	\pm 5 minutes
	Hours 1, 2, 4, 6, 8	\pm 10 minutes
	Hour 24	\pm 60 minutes

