12.3.3 Pharmacokinetics

Plasma concentrations will be listed at each time point by subject, and summarized by treatment at each time point using descriptive statistics (n, mean, standard deviation, coefficient of variation, median, minimum and maximum values). PK calculations will be performed based on actual time of blood sample collection, using non-compartmental methods with WinNonlin Version 6.3.1 or higher (Certara Corporation, Princeton, New Jersey, USA). PK parameters will be listed by subject and summarized by cohort. In addition to the descriptive statistics listed above, geometric means will be reported for the PK parameters.

All plasma concentrations below the lower limit of quantitation (BLOQ) for the assay that occur prior to the first or after the last quantifiable timepoint will be treated as “0” in the PK analyses and summary statistics. Plasma concentrations that are BLOQ but occur between quantifiable timepoints will be set to missing.

The PK endpoints will be listed and summarized for each dosing route and cohort. The arithmetic means, geometric means, medians, minimums and maximums, CV% will be displayed.

Plots of mean concentration levels and individual subject concentrations versus time will also be prepared.

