4.1.2 Pharmacokinetic Measurements

The PK measurements in each dosing cohort are the assessments of plasma concentrations of atorvastatin and its metabolites (2-hydroxy atorvastatin and 4-hydroxy atorvastatin) in the oral administration and the administrations by the injectable route.

At the oral PK visit (Screening Period), serial PK blood samples to measure plasma concentrations of atorvastatin and its metabolites will be collected within 60 minutes prior to taking the oral dose of atorvastatin, at 30 minutes (\pm 5 minutes), 1, 2, 4, 6, and 8 h (\pm 10 minutes) after taking the oral dose.

Levels of atorvastatin and metabolites measured from the pre-dose (oral) timepoint are imputed as 24-hour levels since the subject is on daily, constant dosing.

In the last dose of injectable atorvastatin at Day 15 visit, serial PK blood samples to measure plasma concentrations of atorvastatin and its metabolites will be collected within 60 minutes prior to the start of the dose, immediately after completion of IV dose (within 3 to 7 minutes), at 30 minutes (\pm 5 minutes), 1, 2, 4, 6, and 8 h (\pm 10 minutes) after completing the injected dose.

Levels of atorvastatin and metabolites measured from the pre-dose (IV) timepoint are imputed as 24-hour levels since the subject is on daily, constant dosing.

In the sub-study for the single SC atorvastatin dose, serial PK blood samples to measure plasma concentrations of atorvastatin and its metabolites will be collected at 30 minutes (\pm 5 minutes), 1, 2, 4, 6, 8 (\pm 10 minutes) and 24 h (\pm 60 minutes) after the SC dose.

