5.7.3 Relative Bioavailability Analysis

To compare the PK profile of atorvastatin and metabolites administered by the IV or SC route to that of oral administration, the relative bioavailability analysis will be performed for each cohort using key PK parameters (C_{max} , AUC_{0-24} and AUC_{inf}) of atorvastatin and, if data allow, its metabolites. Dose-normalized key PK parameters of the oral and IV (or SC) routes of administration will be log-transformed and analyzed using an analysis of variance (ANOVA) model including terms for treatment route as a fixed effect and subject as a random effect. The least squares geometric means ratio of atorvastatin oral vs IV (or SC) will be calculated. A 90% CI on the ratio of untransformed PK parameters will be derived through reverse transformation of the 90% CI for the difference in the log scale to the 90% CI for the ratio in the original scale.

When appropriate, the same analysis may be performed to compare the PK profile of the atorvastatin SC vs oral (Cohort 4).

The least-squares geometric means, ratio of the geometric means and 90% CIs on the ratio will be displayed.

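### SAP 5.7.2 places the first post-IV sample at 0.0055 h although it is drawn 3 to 7 minutes after dosing, and gives no C0 or trapezoidal rule

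*SAP*

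**What the plan says.** SAP 5.7.2 gives a general time rule: "Pharmacokinetic parameters will be calculated using noncompartmental methods and actual blood sampling times". It adds a fallback: "In case of missing actual time, planned (or nominal) time will be used". Later in the same section comes a fixed value for one sample: "The first timepoint immediately following IV bolus dosing is set as 0.0055 hour (assume 20 seconds bolus dosing".

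SAP 4.1.2 schedules that sample "immediately after completion of IV dose (within 3 to 7 minutes", and protocol Table 9-3 gives its window as "3 to 7 minutes following the end of the administration". Protocol 12.3.3 agrees with the general rule: "PK calculations will be performed based on actual time of blood sample collection". Protocol 9.3.4 shows that the times will be available: "The actual sample collection date and time is entered in the eCRFs".

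The IV parameters are then used in SAP 5.7.3, where "the relative bioavailability analysis will be performed for each cohort using key PK parameters", namely Cmax, AUC0-24 and AUCinf, with an oral-to-IV ratio and 90% CI. For the calculation, both documents name non-compartmental methods in WinNonlin. Neither states a trapezoidal rule or how the concentration at time zero after an IV bolus is obtained.

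**The concern.** The value 0.0055 h is the end of an assumed 20-second injection. Using it treats blood drawn minutes later as if it had been drawn the moment the injection stopped. That is neither the actual time nor a planned time inside the window, so it fits neither of the section's own rules.

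Concentration falls fastest just after a bolus, so the time given to this point shapes any back-extrapolated C0 and the area up to 0.5 h. It therefore enters IV AUC0-24 and the oral/IV AUC ratio. It would also enter clearance and VDss if these are derived from that AUC, which the SAP does not spell out. Because the draw time is ignored, two identical profiles sampled at 3 and at 7 minutes would give different AUCs. Wherever the first sample is the peak, IV Tmax is set by the rule, but Tmax is not among the listed endpoints.

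**Working it through.** **1. The plan's figure.** 20 s / 3600 = 0.00556 h, and 0.0055 × 3600 = 19.8 s. The figure reproduces, truncated rather than rounded.

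**2. Against the window.** 3/60 = 0.050 h and 0.050/0.0055 = 9.1. 7/60 = 0.117 h and 0.117/0.0055 = 21.2. The assigned time is 9 to 21 times too early.

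**3. How the time acts (hand example).** Assume the 0.5 h concentration is 0.2 of the first sample (C1 = 1), a 5-minute draw (0.0833 h), log trapezoid and back-extrapolated C0. Slope k = ln(C1/C0.5)/(0.5 − t); C0 = C1·exp(k·t); AUC0-0.5 = (C0 − C0.5)/k.

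| Time used | k (per h) | C0 | AUC0-0.5 |
|---|---|---|---|
| 0.0833 h | 1.609/0.4167 = 3.863 | 1.380 | 1.180/3.863 = 0.305 |
| 0.0055 h | 1.609/0.4945 = 3.255 | 1.018 | 0.818/3.255 = 0.251 |

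C0 falls by 26% and AUC0-0.5 by 18%. This is only the first half hour, so the effect on AUC0-24 is much smaller.

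**4. Effect on AUC0-24.** The documents give no half-lives, so 36 steady-state bi-exponential shapes were assumed: distribution half-life 0.1, 0.2 or 0.5 h; terminal half-life 4, 7, 10 or 14 h; intercept ratio A/B of 5, 20 or 50. Samples are at the first draw, then 0.5, 1, 2, 4, 6 and 8 h, with the pre-dose value used at 24 h as the SAP directs. True AUC0-24 = A/α + B/β. For a 5-minute draw, the error against true AUC is:

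| AUC rule, time-zero rule | 0.0055 h | Recorded time | Shapes where 0.0055 h is closer |
|---|---|---|---|
| Log-down, back-extrapolated C0 | -14.1 to +0.5% | +0.6 to +2.3% | 20/36 |
| Log-down, pre-dose at zero | -14.7 to +0.4% | -12.5 to -0.2% | 26/36 |
| Linear, back-extrapolated C0 | +2.9 to +13.6% | +3.6 to +25.5% | 36/36 |
| Linear, pre-dose at zero | +2.8 to +13.4% | +2.2 to +12.7% | 0/36 |

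Under log-down with back-extrapolated C0:
- 0.0055 h against the recorded time changes AUC0-24 by a median of -2.4% (oral/IV ratio +2.5%). The change is under 5% in 25/36 shapes and over 10% in 2/36, at most -16%. By distribution half-life the medians are -5.1% (0.1 h), -4.0% (0.2 h) and -1.6% (0.5 h).
- Absolute error with 0.0055 h against the recorded time: median 1.1% against 1.5%, mean 2.7% against 1.4%, maximum 14.1% against 2.3%, over 5% in 7/36 against 0/36.

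**5. Spread from draw time alone.** For one profile drawn anywhere from 3 to 7 minutes, (max − min AUC0-24)/true AUC was calculated. Under log-down with back-extrapolated C0 it is 0.4 to 13.3% (median 2.2%) with 0.0055 h, against 0.02 to 3.1% (median 0.3%) with the recorded time, which is tighter in 36/36 shapes. Under linear with back-extrapolated C0 it is again tighter in 36/36. With the pre-dose value at zero it is not: 4/36 (log-down) and 0/36 (linear).

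**6. Metabolites.** First-order formation from each parent shape, with assumed elimination half-lives of about 1, 3, 8 and 15 h (144 cases), log-down and pre-dose at zero: 0.0055 h against 5 minutes changes AUC0-24 by 0.01 to 1.3% (median 0.1%).

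**The case against.** The best defence is that 0.0055 h is a nominal value. Table 9-3 has a target column as well as a window, and the target is straight after the dose. SAP 5.7.1 also needs planned times for its mean plots. This does not rescue the sentence. SAP 4.1.2 equates that target with 3 to 7 minutes, 0.0055 h lies outside that window, and the sentence sits among the parameter-calculation rules without being limited to missing times.

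Other objections stand in part:
- Net harm to AUC from the time error alone is not shown. Three of the four rule pairs favour 0.0055 h in most shapes, so deleting the sentence and nothing else could worsen AUC.
- The tail comes from the edge of the grid: 6 of the 7 shapes with error above 5% have intercept ratio 50, and all 7 have a distribution half-life of 0.2 h or less. The documents do not favour these shapes over others.
- The gain in draw-time spread needs back-extrapolated C0 and good clocks. If elapsed times may be off by up to 1 minute (an assumption), the recorded-time spread rises to a median of 1.8% and a maximum of 12.6%, close to the 2.2% and 13.3% with 0.0055 h, though still tighter in 34/36 shapes.
- No decision depends on this. The PK comparison has no acceptance margin, and the missing C0 and trapezoidal rules alone would be a request for detail.

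**Conclusion.** The concern holds, as a minor point. The contradiction is plain in the text and needs no assumption: a stated calculation rule puts a wrong time into IV AUC and the oral/IV AUC ratio, against the plan's own actual-time rule and with the right times on file. The numerical effect is uncertain and usually a few percent. Its size and direction depend on C0 and AUC rules that the plan does not state, and every percentage rests on the assumed shapes. Under log-down with back-extrapolated C0, the fixed time costs a long error tail and a dependence on draw time, while its typical error is no worse. Observed Cmax and its ratio, the subcutaneous results in Cohort 4 and the LDL-C endpoints are unaffected.

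**What to change.** Delete the 0.0055 h sentence from SAP 5.7.2. Analyse the first post-IV sample at its recorded time after the end of injection; if that time is missing, use 5 minutes, the midpoint of the window.

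State the AUC and C0 rules in the same edit. One workable wording:

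> AUC uses linear-up/log-down. For IV parent atorvastatin, C0 is back-extrapolated from the first two post-dose concentrations (first observed value if these do not decline). For metabolites, the pre-dose value is used at time zero.

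Over 3 to 7 minute draws in the assumed shapes, this keeps parent AUC0-24 within +0.2% to +3.8% of true, against -20% to +0.9% with 0.0055 h under the same rules. The choice of method is the sponsor's; what is needed is that one is stated.

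Deleting the sentence also removes the 20-second assumption, which otherwise has to be reconciled with the 5 to 10 seconds in protocol 8.3.2.1.

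The cost is SAP wording and a WinNonlin re-run with times already in the eCRF; no new data are needed. The back-extrapolated C0 remains an estimate (0.1 to 20% below true C0 with a 5-minute draw), and the typical AUC error does not shrink. The gain is correct times, a much narrower worst case and less spread from draw time.
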